In the general population, there is a growing body of literature that demonstrates the effectiveness of PAP in improving systemic blood pressure and several longitudinal observational studies showing that PAP therapy is associated with decreased fatal and non-fatal cardiovascular events.

Additionally, PAP has been shown to reduce biomarkers of oxidative stress and inflammation. Most studies report a reduction in TNF- $\alpha$ , IL-6, and hs-CRP within 2-4 weeks of therapy; a few show no effect. Obesity, cardiovascular disease, smoking status, asthma, and other inflammatory conditions confound the association between SDB and systemic inflammation; many of the studies that do not report any improvement in inflammatory biomarkers with PAP may not have adequately addressed these confounders. Two small studies have given conflicting results about effects of PAP on adiponectin levels. One found an increase in adiponectin levels after 14 days of PAP therapy while another observed no change from baseline levels. Adhesion molecules including VCAM-1 have been shown to decrease with PAP therapy.

The SCI population is uniquely at risk for chronic inflammation. Studies in SCI have shown elevated hs-CRP levels in addition to increased VCAM-1, endothelin-1, and IL-6 levels. The crossroads of SCI and SDB may well represent an elevated pro-inflammatory state that predisposes to CVD disease burden. Reducing systemic inflammation is likely to be beneficial. **There is no information on the impact of PAP therapy on these inflammatory markers in the SCI population with SDB. Our proposal is the first to evaluate this association and determine the therapeutic impact of PAP in this uniquely vulnerable population.**

*F) Impact of PAP on Mood, Sleep Quality, and Quality of Life in the General Population*

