### Study Population:

We will perform unattended portable level II PSG on SCI participants from the Miami and Detroit study sites (100 from each site) who meet the following eligibility criteria:

*Inclusion Criteria:*

- Chronic tetraplegia or paraplegia (C4-L1), American Spinal Injury Association (ASIA) Impairment Scale A, B, C and D
- 18 years and older
- At least one year post injury
- Hearing and vision suitable for comprehension of instructions, and perception of cognitive test stimuli
- No color blindness as measured by a brief screen with color perception Ishihara cards
- Stable medical condition for 2 weeks prior to enrollment. Patients admitted to hospital will be eligible for enrollment if the acute illness precipitating admission is in recovery phase for 2 weeks or longer

*Exclusion Criteria:*

- Diagnosis of SDB and successful positive airway pressure (PAP) therapy prior to injury. Those with a diagnosis of SDB post injury who are not receiving therapy for SDB (PAP, surgical, and/or oral appliance) are eligible for study enrollment
- Patients who are intubated, have a tracheostomy, and/or are using long term invasive/non-invasive positive pressure ventilation
- Participants with predominant central sleep apnea on PSG requiring bi-level PAP therapy
- Severe traumatic brain injury (GCS < 8 at first assessment)
- Unable to understand or read English at a grade 5 level
- Inability to provide informed consent
- Evidence of advanced neurological or systemic disease that may affect cognitive functioning (e.g., Alzheimer's disease, Dementia, Parkinson's disease)
- Significant aphasia or language impairments

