**Baseline Measurements All Subjects:** At the Miami and Detroit sites the study RA will approach SCI individuals identified by the study PI and Co-investigators to determine eligibility for participation in the study. Upon consent, we will ask participants to complete several questionnaires detailed below. We will schedule participants for a single night unattended portable home PSG within one week of enrollment to evaluate sleep architecture and diagnose SDB. The RA at each site will review medical records to document medical and psychological co-morbidities, medication use, laboratory data, spinal cord injury level, ASIA classification, and duration of injury. We will interview participants during their enrollment visit to obtain a medical/sleep history, and anthropometric measures (height, weight, neck circumference, and abdominal girth at end expiration). Whenever possible the RA or PI/site PI will complete the international SCI core dataset for each participant. Additionally, we will use the international SCI CV function basic data set to obtain information about CV co-morbidity. Cognitive testing will be completed at baseline on all subjects who complete portable PSG. **Figure 2 outlines study flow and measurements.**

We will obtain the following respiratory measures during PSG: a) AHI: defined as the number of apneas and hypopneas per hour of sleep, b) arousal index (AI): the number of arousals per hour of sleep, c) percentage of total sleep time (TST) spent with arterial oxygen saturation (Sa-O2) < 90%, d) mean minimum Sa-O2, and e) oxygen desaturation index 4% (ODI4), defined as the number of four percent desaturation events per hour of study time. Respiratory and sleep architecture definitions will be scored according to accepted criteria put forth by the American Academy of Sleep Medicine (AASM). We will define SDB as an AHI  $\geq 10$ . We will score hypopneas initially using alternative rules (>50% reduction in airflow with 3% desaturation or arousal). We will rescore using recommended rules (>30% reduction in airflow with 4% desaturation). In the sleep research community, there is currently no clear consensus on which scoring method is preferred. SDB prevalence rates reported in the literature differ depending on the definition used. Consequently, we will perform all analyses with both definitions in mind and report any differences in observed associations.

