#### Primary Hypothesis (Specific aim 1, Hypothesis 1b)

A test of the primary null hypothesis, that PAP intervention does not increase mean PASAT score against the 1-sided alternative hypothesis that PAP intervention increases mean PASAT, will be based on a general linear model (GLM). PASAT score is modeled as a function of PAP intervention, using an indicator variable with 1 indicating PAP and 0 the sham treatment. A 1 degree of freedom test based on an F statistic will be used to test for a positive coefficient for the PAP indicator. This modeling approach provides a unified framework that accommodates covariates including use of sedating medications, years of education, level of injury, duration of injury, pain severity, presence of anxiety or depression, compliance with PAP, and recruitment center, each of which may reasonably be anticipated to influence PASAT score. We plan to include these covariates in our primary hypothesis test, which will be carried out at  $\alpha = 0.05$ . If the null hypothesis of no effect is rejected, computation of 95% confidence limits on the estimate of treatment difference in PASAT score mean will be carried out.

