#### Secondary Hypotheses

A second phase of analysis will focus on CV biomarkers and measures of sleep quality, quality of life, mood and pain. These analyses are considered exploratory in nature and hence will benefit from comparisons within as well as between groups.

For within group contrasts, initial observations serve as baseline for assessing the effect of treatment at 4 months. As in a classical paired design, inference focuses on the difference between baseline and 4 month observations. Hence, individuals serve as their own control for an effect of intervention. The null hypothesis that the baseline does not differ from the 4 month measurement is tested using statistical methods for a paired design. For normally distributed measurements, a paired t test will be used. For variables that depart from normality and cannot be transformed to approximate normality, a Wilcoxon signed rank test will be used.

Comparisons between PAP and sham treatment groups at 4 months will be made based on the linear model described above for the primary endpoint. In contrast to PASAT, however, tests for treatment group differences of CV biomarkers and measures of sleep quality, HRQOL, mood and pain will be 2-sided. Because the number of secondary hypotheses to be tested is potentially large, these tests will be considered exploratory in nature. Accordingly, control of the false positive inference rate for these tests will be carried out at the group level, as described below, rather than for the entire set of secondary analyses. Similar approach will be taken for the analyses of select measures at the one month time-point.

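### The PAP versus sham biomarker comparison borrows the model built for PASAT, which omits the baseline marker value and the determinants of inflammation that the protocol itself names; the cost is precision, not bias.

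*Combined protocol and SAP*

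**What the plan says.** Hypothesis 2a (Objectives/Specific Aims/Hypotheses) is that four months of PAP improves hs-CRP, TNF-alpha, VCAM-1, adiponectin and 8-isoprostane compared with sham. The Secondary Hypotheses section gives the between-arm analysis in one sentence: "Comparisons between PAP and sham treatment groups at 4 months will be made based on the linear model described above for the primary endpoint". These tests are two-sided and called exploratory. The section on control of the false positive rate also calls them pre-planned and applies a 5% false discovery rate within each category.

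The model referred to is in the Primary Hypothesis section. Besides the treatment indicator and use of sedating medications, its covariates are "years of education, level of injury, duration of injury, pain severity, presence of anxiety or depression, compliance with PAP, and recruitment center", justified as "each of which may reasonably be anticipated to influence PASAT score". No baseline value of the outcome is listed.

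Background section E, on cardiovascular effects of PAP, names a different set of factors for these markers: "Obesity, cardiovascular disease, smoking status, asthma, and other inflammatory conditions confound the association between SDB and systemic inflammation". It adds that "many of the studies that do not report any improvement in inflammatory biomarkers with PAP may not have adequately addressed these confounders".

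Much of the relevant information is collected. Baseline Measurements lists "anthropometric measures (height, weight, neck circumference, and abdominal girth at end expiration"), comorbidities, medication, and an international data set on cardiovascular function in SCI. The Biomarkers section measures every marker before PAP as well as at month 4.

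**The concern.** The protocol attributes some earlier null results to poorly handled determinants of inflammation, then analyses the same kind of marker with covariates chosen for a cognitive test. Years of education has an obvious place in a PASAT model and little in a model for hs-CRP. Body size, cardiovascular disease and the participant's own pre-treatment level are the natural predictors of a month-4 marker, and none is named.

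At stake is the sensitivity of Hypothesis 2a. No power, SD or effect size is given for any biomarker, the sample size was set for PASAT, and five markers share one false discovery rate. Precision is therefore scarce, and the plan leaves some of it unused. With no biomarker covariates prespecified, any that are added later will be chosen after the data are seen.

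**Working it through.** **Does the inherited model cover the named factors?**

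| Factor | In the PASAT model? | Measured at baseline? |
|---|---|---|
| Obesity | No | Yes (height, weight, girth) |
| Cardiovascular disease | No | Yes (cardiovascular data set, comorbidities) |
| Smoking | No | Not named |
| Asthma, other inflammatory conditions | No | Only under general comorbidity review |
| Baseline value of the marker | No | Yes |

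None is handled by design either. Randomization Protocol gives 1:1 allocation within centre and no other stratification, and the eligibility criteria exclude none of the factors named in Background section E.

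**The plan's own figure.** There is none for biomarkers. The only stated power is for PASAT (40 per arm, difference 7, SD 9, alpha 0.05: 0.93). A two-sided two-sample t calculation returns 0.930, so the same method is used below.

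**Detectable difference.** For 80% power at two-sided 0.05, the standardized difference must be 0.57 at 50 per arm, 0.63 at 40 and 0.74 at 30 (30 being 50 less the plan's 40% for non-adherence or loss). At the strictest false discovery step for five markers, 0.05/5 = 0.01, it must be 0.70, 0.78 and 0.91.

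**Chance imbalance.** Input: 31% obese, from the review of veterans with SCI in Background section A. Applying it to the randomized participants is an assumption. With two independent binomial counts, the exact probability that the arms differ by at least 10 percentage points is 0.33 at 50 per arm, 0.40 at 40 and 0.49 at 30.

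**Precision gained (assumed correlations and R-squared; degrees-of-freedom loss ignored).** The standard error is multiplied by sqrt(1 - R²).

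- Baseline marker alone, correlation 0.6: sqrt(1 - 0.36) = 0.80, a 20% cut, worth 1/0.64 = 1.56 times the sample. Over correlations of 0.4 to 0.7 the factor runs from sqrt(0.84) = 0.917 to sqrt(0.51) = 0.714, a cut of 8-29%.
- BMI and cardiovascular disease alone, R² of 0.10 to 0.30: sqrt(0.90) = 0.949 to sqrt(0.70) = 0.837, a cut of 5-16%.
- Both together, treating BMI and cardiovascular disease as stable factors explaining R² at each visit, with overall correlation 0.6. The correlation left after adjusting for them is (0.6 - R²)/(1 - R²), and the residual variance is (1 - R²)(1 - that correlation squared).
  - R² = 0.10: 0.5/0.9 = 0.556; 0.9 × (1 - 0.309) = 0.622.
  - R² = 0.30: 0.3/0.7 = 0.429; 0.7 × (1 - 0.184) = 0.571.
  - Relative to 0.64 for the baseline value alone: sqrt(0.622/0.64) = 0.986 and sqrt(0.571/0.64) = 0.945, a further cut of 1.4-5.5%.

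**In terms of power.** For a true standardized difference of 0.6 (assumption) at two-sided 0.05:

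| Per arm | No adjustment | R² 0.10 | R² 0.30 | Baseline value, correlation 0.6 |
|---|---|---|---|---|
| 40 | 0.755 | 0.798 | 0.886 | 0.912 |
| 30 | 0.63 | 0.67 | 0.78 | 0.815 |

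Most of the gain comes from the baseline marker value.

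**The case against.** **Randomization already deals with confounding.** The Background statement concerns the association between SDB and inflammation, whereas Hypothesis 2a is a randomized contrast. A reader might infer that the named factors bias the PAP versus sham comparison. They do not: they are balanced in expectation and the type I error is unaffected. In the within-arm paired tests, stable traits such as long-standing obesity or smoking cancel. This objection stands and limits the point to precision and chance imbalance.

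**The covariate list may not carry over.** The Primary Hypothesis section introduces the list as open-ended and commits to it for the primary test, so the biomarker covariates may simply be unspecified. That is a fair reading, but under it too no biomarker covariates are prespecified.

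**The endpoints are exploratory.** True, and the PASAT result is untouched. They are nevertheless described as pre-planned, with formal error control, and serve a stated hypothesis.

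**A tempting stronger reading.** Entry requires "Stable medical condition for 2 weeks prior to enrollment", and the fasting, caffeine, alcohol and time-of-day rules for blood collection include no illness check. A reader might infer that baseline samples are free of acute illness and month-4 samples are not, so that the paired tests drift towards worsening. The documents do not establish this. The stability rule attaches to enrollment, while the first sample is taken at randomization. The same criterion admits hospital patients recovering from an acute illness, whose markers could be raised at baseline and fall by month 4. The net direction depends on the inpatient mix and the incidence of illness, and neither is given.

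**Conclusion.** The point holds as a loss of efficiency in secondary endpoints. The model assigned to the biomarker comparison was built for a cognitive score and omits both the baseline marker value and the determinants of inflammation that the protocol names. There is no systematic bias between arms, and no shift in the paired tests can be claimed.

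The 33% chance of a 10-point obesity imbalance at 50 per arm rests on carrying the 31% prevalence over to this sample. The 20% reduction in standard error rests on an assumed correlation of 0.6. The figures for BMI and cardiovascular disease rest on an assumed 10-30% of variance, and on stability between visits for the increment over baseline. The lack of a biomarker-specific model is clear from the text; the size of the gain is illustrative.

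**What to change.** For the biomarker category, prespecify a linear model for the month-4 marker with treatment, recruitment centre, the baseline value of the same marker (transformed where needed, as Planned analyses already allows), baseline BMI or abdominal girth, and cardiovascular disease. Add smoking and inflammatory conditions where the baseline history records them; the sponsor should confirm this, since Baseline Measurements does not name smoking. PASAT-specific covariates such as years of education need not be carried over. PAP compliance, which is measured after randomization, is not part of this proposed model.

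The cost is SAP wording and a few degrees of freedom. The core terms use data already planned for collection.

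Separately, Study Overview, the inclusion criteria and the blood collection section set no acute-illness condition for either draw. Those sections should be reconciled; no particular sampling rule is proposed here.

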#### Control of False Positive Rate of Inference

The inference of primary interest in this study is the effect of treatment on PASAT score. Because the test for intervention on PASAT is considered pre-planned, it will be carried out at  $\alpha$ -level 0.05. Similarly, tests for effects on groups of CV biomarkers, sleep, mood and quality-of-life measurements

are considered pre-planned in the sense that measurements in each group will be subjected to statistical testing regardless of test outcome for PASAT. Accordingly, tests for multiple measurements taken in each category of biomarkers will be carried out at  $\alpha$ -levels below 0.05. This approach recognizes that multiple testing is involved within each biomarker category and adjusts the significance level for individual tests downward to control the false positive inference rate at the category level. We will apply a False Discovery Rate (FDR) criterion of 5% separately for each category, thereby acknowledging the substantial overall number of tests per category but preserving power to detect true effects for each type of biomarker.

Primary analyses will be conducted in accordance with the intention-to-treat principle. We will also repeat analyses using a per protocol viewpoint. We will use statistical software, SPSS for Windows version 19 for all analyses.

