## Research Strategy and Study Design

### Study Overview:

During the 4-year study period we will screen 200 SCI participants who meet eligibility criteria and consent to participate with portable level II polysomnography (PSG) and randomize 100 subjects who have SDB to auto-PAP or sham PAP. Participants will be recruited from the University of Miami (Miami Project to Cure Paralysis), the Miami VA, Wayne State University (Michigan Rehabilitation Institute), and affiliated Detroit VA through their outpatient SCI clinics and/or inpatient rehabilitation units. Participants will be asked to complete questionnaires measuring sleep quality (SQ), SDB risk, insomnia severity, daytime sleepiness, pain severity, mood, and HRQOL. They will undergo an overnight, at home (or if hospitalized, in the hospital room) portable unattended PSG performed at their normal sleep time. Subjects with an apnea-hypopnea index (AHI)  $\geq 10$  events/hr will be randomized to receive 4 months of auto-PAP therapy or PAP set at a fixed pressure of 3 cmH20 (sham PAP).

We will perform neuro-psychological evaluations prior to randomization on all participants who complete a portable PSG to evaluate general and pre-morbid function, immediate verbal memory, simple and sustained attention, processing speed, and executive function. Selection of these particular cognitive measures reflects impairments in these domains observed in patients with SDB within the general population. These domains are also impaired in patients with acute and chronic SCI. **Importantly, none of the cited SCI studies have examined the potential role of SDB in cognitive impairment in SCI participants.**

One cognitive measure (PASAT) and 3 sleep questionnaires (PSQI, FOSQ and ESS) will be repeated at 1 month follow-up in those randomized to therapy or placebo. Complete neuro-psychological evaluations will be repeated at the 4 month follow-up time point in those with SDB who were randomized to PAP or sham PAP (primary outcomes). All measures obtained from these repeated assessments will be subject to a Reliable Change Index analysis to control for potential practice effects. We will obtain blood and urine samples for measurement of CV biomarkers at time of randomization and the four month follow-up. Additionally, sleep and quality of life questionnaires will be repeated at four month follow-up (secondary outcomes).

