**1) Pre-morbid Functioning:**

WIDE RANGE ACHIEVEMENT TEST – IV (READING SUBTEST): The WRAT-IV Reading Subtest is a norm-referenced test that measures the basic academic skill of word reading. It was standardized on a representative national sample of over 3,000 individuals ranging in age from 5 to 94 years. Higher scores are indicative of better sight reading abilities and can serve as a proxy for pre-morbid intellectual functioning.

2) Simple and Divided Attention:

a) DIGIT SPAN SUBTEST OF THE WECHSLER ADULT INTELLIGENCE SCALE –IV: The digit span subtest requires the individual to repeat a series of numbers in the same order, or in reverse order, than orally provided by the test administrator. Low scores on the digit span subtest suggest limited attention, while higher scores indicate a greater ability to concentrate and attend to orally presented information.

b) PACED SERIAL ADDITION TEST (PASAT): The PASAT measures divided, attention and working memory; cognitive domains that have been shown to be particularly salient to SDB. The individual being tested is given single digits at fixed intervals administered by a computer, and needs to add the current number to the last number on each successive presentation. The participant provides verbal responses and the examiner records the responses on a scoring sheet. Lower scores indicate greater impairment of attention.  **The PASAT is the primary outcome measure for this study.**

3) Processing Speed:

SYMBOL DIGIT MODALITIES TEST (SDMT): The SDMT is a substitution task that requires the individual being evaluated to replace symbols with the numbers assigned to them on a reference key. A time limit is imposed to complete the task. Only the oral version of the SDMT will be administered requiring verbal responses. The SDMT has shown excellent reliability, sensitivity, and validity.

4) Memory:

HOPKINS VERBAL LEARNING TEST-REVISED (HVLT-R): The HVLT-R is an assessment of verbal learning and memory, composed of three learning trials, a delayed recall trial, and a delayed recognition trial. It has high test-retest reliability and validity, and has been used in studies of participants with chronic medical conditions. 

5) Executive Function:

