### **Data Analysis:**

Feasibility: The SCI Service at Miami VA actively serves approximately 300 patients. The Miami Project maintains a database of persons who have volunteered their participation in research studies and a database of individuals who have participated in past studies and volunteered additional participation. The database currently contains 3400 persons whose ages and levels of injury match the sought study participants. The Detroit VA SCI service oversees the care of greater than 100 patients/year. The Rehabilitation Institute of Michigan provides care for 350 SCI individuals. We anticipate completion of enrollment by the second quarter of Year 4, with 100 patients enrolled for PSG from each site.

Sample size justification and power: We will recruit 200 participants who meet our eligibility criteria and anticipate an SDB prevalence of 0.50 in SCI participants. This will allow us to randomize 100 participants with SDB to PAP or placebo arm. The neurocognitive test best characterized in both SCI and SDB is the Paced Serial Addition Test (PASAT). The PASAT is our primary study outcome. A mean difference in PASAT scores of 7 discriminates between those with and without cognitive impairment in populations with and without SDB. Assuming a standard deviation of 9 and alpha of 0.05, a sample size of 40 per study arm has a power of 0.93 to detect a mean difference of 7 units. Assuming a PAP non-adherence rate and/or loss to follow-up of 40%, we will continue to have sufficient power (81%) to detect such a difference with our proposed sample size of 100. These findings would be in keeping with PASAT values obtained in non-disabled patients with SDB vs. controls, and PASAT performance in other populations (e.g. multiple sclerosis, mild traumatic brain injury).

Planned analyses: We will score questionnaires while blind to PSG data and group allocation using instructions provided by the questionnaire developer. We will first examine continuous variables for normality. For those variables without a normal distribution, we will explore appropriate transformations in an attempt to achieve normality. Continuous variables will be summarized as means and SD, and categorical variables will be summarized as frequencies. Prevalence of poor SQ will be calculated as the proportion of individuals who complete the PSQI with a score of  $\geq 5$ .

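### The primary PASAT model uses one score per person, omits baseline PASAT and gives no method for missing scores, so an analysis labelled intention-to-treat defaults to those with a month-4 score

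*Combined protocol and SAP*

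**What the plan says.** All places are in the combined protocol and SAP.

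- The test battery under Specific Aim 1 fixes the endpoint: "The PASAT is the primary outcome measure for this study". The battery is given at baseline and at four months.
- Study Overview labels the four-month evaluations as the primary outcomes: "Complete neuro-psychological evaluations will be repeated at the 4 month follow-up time point in those with SDB who were randomized". It also provides an intermediate score: "One cognitive measure (PASAT) and 3 sleep questionnaires (PSQI, FOSQ and ESS) will be repeated at 1 month follow-up".
- Primary Hypothesis defines the test: "PASAT score is modeled as a function of PAP intervention, using an indicator variable with 1 indicating PAP and 0 the sham treatment". It names no visit and has no repeated-measures term. Its covariates are sedating medication, education, injury level and duration, pain, anxiety or depression, PAP compliance and centre. Baseline PASAT is not listed.
- Secondary Hypotheses ties that model to month 4: "Comparisons between PAP and sham treatment groups at 4 months will be made based on the linear model described above for the primary endpoint". It also says that selected 1-month measures will be analysed in a similar way.
- Data Analysis budgets for attrition: "Assuming a PAP non-adherence rate and/or loss to follow-up of 40" per cent.
- Control of False Positive Rate of Inference states: "Primary analyses will be conducted in accordance with the intention-to-treat principle", with a per-protocol repeat.

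No section gives imputation, a longitudinal model or a sensitivity analysis for a missing PASAT score.

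**The concern.** Intention-to-treat says who belongs in the comparison. It does not say what happens when a participant has no outcome. A linear model with one response per person drops anyone without that response unless another rule is written. On a plan that allows for substantial loss, two things are at stake.

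- **Precision.** An earlier score on the same test is usually the strongest predictor of a later one, yet the listed model uses neither the baseline nor the 1-month score.
- **Bias.** If those who leave differ from those who stay, and differ in another way in the other arm, the month-4 contrast among those observed is not the contrast among those randomised. The two earlier scores are the data best placed to correct this, and both are already collected.

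Leaving the rule open also allows it to be chosen after the data are seen.

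**Working it through.** **1. The plan's own figures.** Inputs from Data Analysis: difference 7, SD 9, alpha 0.05, 40 per arm. A two-sample t test gives power 0.930 two-sided (0.964 one-sided), so the stated 0.93 is reproduced as a two-sided calculation. With 40% of 100 removed, 30 per arm give 0.842 two-sided or 0.909 one-sided. The stated 81% is not reproduced, but nothing below depends on it.

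**2. How many scores could be missing.** The 40% is not split. If it is all loss, 100 × 0.6 = 60 participants have a month-4 score. If it is all non-adherence and everyone attends, 100 do. The missing share is therefore between 0 and 40%.

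**3. Precision under random loss.** The documents give no correlation between PASAT visits; 0.7 to 0.8 is assumed. At 40% missing (30 per arm):

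- Unadjusted: SE = SD × √(2/n) = 9 × √(2/30) = 2.32.
- With baseline PASAT: SE ≈ 2.32 × √(1 − r²), which is 2.32 × 0.714 = 1.66 at r = 0.7 and 2.32 × 0.600 = 1.39 at r = 0.8.
- Adding the 1-month score through a likelihood model lowers this by only about 0.04 to 0.06 (simulation below).

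The precision gain thus comes almost wholly from baseline PASAT.

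**4. Bias under outcome-related loss.** Simulation with 50 per arm, SD 9, true effect 3.5 at month 1 and 7 at month 4, and equal correlation 0.7 or 0.8 between visits. Loss is logistic in the 1-month score, slope 0 or ±0.7 per SD, with 3,000 trials per scenario. Three estimates of the month-4 difference are compared: observed means, observed scores adjusted for baseline PASAT, and the likelihood estimate using baseline and 1-month PASAT. Bias is in points at 40% missing, over r = 0.7 to 0.8:

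| Pattern of loss | Unadjusted | + baseline | + baseline and month 1 |
|---|---|---|---|
| Random | about 0 | about 0 | about 0 |
| Same pattern in both arms | about 0 | about 0 | about 0 |
| Low scorers leave sham only | −1.7 to −1.8 | −0.4 to −0.5 | about 0 |
| Low scorers leave PAP only | +1.6 to +1.8 | +0.4 to +0.5 | about 0 |
| Low scorers leave sham, high scorers leave PAP | −3.2 to −3.6 | −0.8 to −1.0 | about 0 |
| High scorers leave sham, low scorers leave PAP | +3.1 to +3.6 | +0.7 to +1.0 | about 0 |

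Repeat runs of the opposite-direction pattern reach 3.7 unadjusted. At 20% missing, the differential patterns give 0.8 to 1.9 unadjusted, 0.2 to 0.5 with baseline, and about 0 with both scores.

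**5. Where the repeated-measures model falls short** (40% missing, low scorers leaving sham and high scorers leaving PAP, unless stated):

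- Half of the leavers go before month 1: a bias of 0.3 to 0.4 remains.
- All go before month 1: 0.7 to 1.0 remains, the same as with baseline adjustment alone.
- Loss depends on the month-4 score itself: 0.7 to 0.9 remains if only sham is affected, and 1.5 to 2.0 in the opposite-direction pattern.

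**The case against.** Several points on the other side are sound.

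- A reader might infer that the plan prescribes a completer analysis. It does not. No exclusion is stated, and the primary model text does not even name the visit. Dropping participants is what a linear model does when the plan is silent.
- A reader might infer that the 1-month PASAT is wasted. Secondary Hypotheses plans a separate 1-month analysis of selected measures, and Study Overview subjects repeated assessments to a Reliable Change Index. The score is outside the primary test only. The index does not close the gap, because it also needs the follow-up score.
- A reader might take 40% as the expected dropout. It combines non-adherence with loss, and non-adherers who attend month 4 stay in.
- A reader might infer that the result will be biased, or biased against PAP. Bias needs loss that is related to outcome and differs by arm, and it can run either way. The sham device, the blinding and the same follow-up procedures in both arms make differential loss an assumption, not a feature of the plan.
- Baseline adjustment alone removes about 70 to 80% of the simulated bias, so most of the unadjusted figures should not be charged to the unused 1-month score. The near-zero bias of the fuller model follows from letting loss depend only on a score that everyone has.
- The unadjusted comparator leaves out the planned covariates. If education, pain and mood predict PASAT, the true starting SE is below 2.3 and the gain is smaller.

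These points limit the size of the finding. They do not supply the missing rule, and they do not put baseline PASAT into the model.

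**Conclusion.** The concern holds in a limited form. The plan promises intention-to-treat, fits one PASAT score per person, lists no baseline PASAT and says nothing about missing scores. The default is an analysis of those with a month-4 score.

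The firmest part is precision, which depends on the correlation assumed but not on any pattern of loss: baseline PASAT takes the standard error from about 2.3 to 1.4–1.7 at 40% missing. Bias is conditional. At the 40% extreme and with loss that differs by arm it is 1.6 to 3.7 points unadjusted. Baseline PASAT brings this to 0.4–1.0, and the 1-month score removes the rest only for people who leave after month 1 and whose leaving depends on that score. With random or matching loss it is nil. The visit correlation, the loss patterns and the 1-month effect are assumptions, since the documents give none of them.

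The change should be made, because the plan is silent on a central matter and the remedy uses data already collected. Nothing here shows that the primary result will be wrong.

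**What to change.** 1. Add baseline PASAT to the primary model.
2. Fit it as a likelihood-based repeated-measures model of PASAT at 1 and 4 months with unstructured covariance. Include arm, visit, arm-by-visit, baseline PASAT-by-visit and centre, and keep the other planned covariates that are measured before randomisation. Name the 4-month arm contrast as the primary test.
3. State that every randomised participant with any post-baseline PASAT contributes to this model.
4. Add one delta-adjusted sensitivity analysis for missing month-4 scores. It should cover participants with no post-baseline PASAT, whom the main model cannot retain.
5. Report loss to follow-up and non-adherence separately by arm, with the timing of loss relative to month 1.

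The cost is SAP wording and slightly more analysis work, with no new data. The price in assumptions is that the main analysis relies on data missing at random given baseline and 1-month PASAT, which is why the sensitivity analysis is needed.
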